6.1.2. AEs, SAEs, MAEs, and NDCMCs

6.1.2.1. Main Analysis

- Estimand strategy: Treatment policy ([Section 2.2.1](#)).
- Analysis set: Safety population ([Section 4](#)).
- Analysis methodology: 95% CI of the proportion of participants reporting such events, using the Clopper-Pearson method ([Section 5.2.1](#)).
- Analysis timing: Day 1 through 4 weeks after vaccination for AEs; Day 1 through 6 months after vaccination for SAEs, MAEs, and NDCMCs.
- Intercurrent events and missing data: All data collected are included. Missing AE dates will be imputed as described in Pfizer's Vaccine Statistics Rulebook.

Reporting results:

- The number of participants with AEs through 4 weeks after vaccination (n), the proportion (%), and the associated 2-sided Clopper-Pearson 95% CIs will be presented for each study intervention group.
- The number of participants with SAEs, MAEs, and NDCMCs through 6 months after vaccination (n), the proportion (%), and the associated 2-sided Clopper-Pearson 95% CIs will be presented for each study intervention group.
- Descriptive statistics, including the proportion (%), the numerator (n) and the denominator used in the proportion calculation, and the 95% CIs for the percentage using the Clopper-Pearson method, will be presented for each SOC and each PT within each SOC for each study intervention group.

6.1.2.2. Sensitivity/Supplementary Analyses

To support the assessment of AEs, the endpoints below as specified in [Section 3.1.3](#) will be summarized with the same analysis population using the same presentation as specified in the main analysis:

- Immediate AEs

- Related AEs
- Severe AEs
- Life-threatening AEs
- AEs leading to study discontinuation/withdrawal
- AEs leading to death
- AESIs

All AEs/SAEs occurring after informed consent and prior to vaccination will not be included in the analyses but will be listed.

In addition, any AEs occurring up to 48 hours after blood draws will be listed.

6.2. Secondary Endpoint(s)

6.2.1. HAI Titers for the 2023-2024 Northern Hemisphere Seasonal Strains Recommended by WHO for CCI Influenza Vaccines

6.2.1.1. Main Analysis

- Estimand strategy: Hypothetical approach ([Section 2.2.2](#)).
- Analysis set: Evaluable immunogenicity population (HAI CCI) ([Section 4](#)).
- Analysis methodology: Descriptive summary statistics ([Section 5.2.1](#) and [Section 5.2.2](#)).
- Analysis timing: Day 1 prior to study intervention administration (HAI GMTs, HAI titers $\geq 1:40$) and at 4 weeks after vaccination.
- Intercurrent events and missing data: All data collected after or at intercurrent events will be excluded ([Section 2.2.2](#)). Antibody titers below the LLOQ, denoted as BLQ, or below the LOD will be set to $0.5 \times \text{LLOQ}$ for analysis ([Section 5.3.2](#)). Missing data will not be imputed. Immunogenicity data that are confirmed as not valid will not be used for analysis.

Reporting results:

- Descriptive statistics, including the sample size (n), HAI GMTs, HAI GMFRs, and 95% CIs for the HAI GMTs and HAI GMFRs, will be presented for each strain and each study intervention group ([Section 5.2.2](#)).

- Descriptive statistics, ie, HAI GMRs of each tIRV (tIRV1, tIRV2 and tIRV3) group compared with each control group (QIV1, qIRV1) at 4 weeks after vaccination, and the 95% CIs for the HAI GMRs, will be presented for each strain ([Section 5.2.2](#)).
- The proportion of participants achieving HAI seroconversion for each strain at 4 weeks after vaccination, and the associated 2-sided Clopper-Pearson 95% CIs, will be provided by study intervention group.
- The proportion of participants with HAI titers $\geq 1:40$ for each strain before vaccination and at 4 weeks after vaccination, and the associated 2-sided Clopper-Pearson 95% CIs, will be provided by study intervention group.
- Empirical RCDCs will be plotted by study intervention group.
- HAI GMTs for each strain, and the associated 95% CIs, will be plotted by study intervention group.
- HAI seroconversion rate for each strain, along with the associated 95% CIs, may be plotted by study intervention group.

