## 2. INTRODUCTION

### 2.1. Study Rationale

The WHO recommendation for the composition of influenza virus vaccines in the 2023-2024 northern hemisphere influenza season includes both a quadrivalent and a trivalent vaccine, differing by the presence/absence of the B/Yamagata lineage, considering that the B/Yamagata lineage has not been seen in circulation since March 2020. At the 05 October 2023 VRBPAC meeting, the committee recommended to move to trivalent influenza vaccines excluding the B/Yamagata lineage from strain compositions. Thus, this study will mainly assess trivalent modRNA vaccine formulations targeting 2 influenza A virus types (H1N1 and H3N2) and 1 influenza B virus (B/Victoria lineage).

Pfizer is currently developing an mRNA-based influenza vaccine, which has been administered to younger (18 through 64 years of age) and older ( $\geq 65$  years of age) adults in several clinical studies, as described in the IB. Immunogenicity data from these studies suggest that influenza A strain HAI and cell-mediated (both CD4 and CD8) responses are comparable to or better than those observed following vaccination with a licensed influenza vaccine, though the influenza B HAI responses following vaccination with qIRV are somewhat attenuated. The purpose of Substudies A and B is to evaluate the safety and immunogenicity of additional influenza modRNA vaccine candidates optimized to enhance immunogenicity against influenza B viruses while maintaining or enhancing vaccine-induced immunogenicity against influenza A viruses.

Substudy C will assess the safety CCI of a quadrivalent modRNA vaccine targeting CCI in older adults ( $\geq 65$  years of age). CCI

the CCI safety of vaccines containing CCI, Substudy C will explore CCI

CCI

These assessments will be conducted across 3 substudies:

- Substudy A: a Phase 2, randomized, observer-blinded (sponsor-unblinded) substudy to evaluate the safety, tolerability, and immunogenicity of 3 different formulations of tIRV encoding HA for the targeted seasonal strains compared to licensed influenza vaccines and qIRV1 (encoding HA for 2 A and 2 B seasonal strains) in healthy adults 18 through 64 years of age.

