### 10.11.2. Introduction (Substudy A)

#### 10.11.2.1. Substudy A Rationale

Ongoing and completed influenza modRNA vaccine studies demonstrated attenuated influenza B strain responses in adults 18 through 64 years of age. Substudy A is a Phase 2, randomized, active-controlled, observer-blinded (sponsor-unblinded) study to assess the safety, tolerability, and immunogenicity of different formulations and doses of tIRV (2×A, 1×B) aimed at enhancing the immunogenicity against influenza B strains compared to a licensed CCI influenza vaccine. This substudy will be conducted in adults 18 through 64 years of age and will assess the following formulations and doses of tIRV:

- tIRV1 (preformulated) – CCI [REDACTED]
- tIRV2 (separate LNPs for each strain) – CCI [REDACTED]  
[REDACTED]
- tIRV3 (separate LNPs for each strain) – CCI [REDACTED]  
[REDACTED]

This substudy will inform the choice of the optimized influenza modRNA vaccine reformulation that may be further studied in adults 18 through 64 years of age.

See [Section 10.11.4](#) for more details regarding the design.

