#### 10.11.9.1.2. Multiplicity Adjustment

There is no multiplicity adjustment for Substudy A, as all analyses are descriptive in nature.

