5. GENERAL METHODOLOGY AND CONVENTIONS

5.1. Hypotheses and Decision Rules

The study is descriptive in nature, no formal statistical hypothesis testing will be performed. No decision rules will be applied.

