5.2. General Methods

CI for all endpoints in the statistical analysis will be presented as 2-sided at the 95% level unless specified otherwise.

The safety analyses are based on the safety population. Participants will be summarized by vaccine group according to the study interventions they actually received. Completely missing reactogenicity e-diary data will not be imputed; missing AE dates will be handled according to the Pfizer safety rules.

For the immunogenicity endpoints, the main analysis will be based on the evaluable immunogenicity population. Antibody titers below the LLOQ, denoted as BLQ, will be set to $0.5 \times \text{LLOQ}$ for GMT analysis. No other missing assay data will be imputed in the analyses. All immunogenicity analyses will be performed after the imputation of the antibody titers that are below the LLOQ.

An additional analysis may be performed based on the mITT immunogenicity populations if there is a large enough difference ($>10\%$) in sample size between the mITT immunogenicity population and the evaluable immunogenicity population. Participants will be summarized according to the vaccine group to which they were randomized. Missing serology data will not be imputed.

No formal multiplicity adjustments will be applied for the analyses in multiple endpoints or for multiple looks of the same endpoint due to the descriptive nature of this substudy.

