5.2.2.3. Geometric Mean Ratios

The GMR will be calculated as the mean of the difference of logarithmically transformed assay results and exponentiating the mean. Two-sided CIs will be obtained by calculating CIs using the Student t distribution for the mean difference of the logarithmically transformed assay results and exponentiating the confidence limits.

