6.2.1.1. Main Analysis

- Estimand strategy: Hypothetical approach ([Section 2.2.2](#)).
- Analysis set: Evaluable immunogenicity population (HAI CCI) ([Section 4](#)).
- Analysis methodology: Descriptive summary statistics ([Section 5.2.1](#) and [Section 5.2.2](#)).
- Analysis timing: Day 1 prior to study intervention administration (HAI GMTs, HAI titers $\geq 1:40$) and at 4 weeks after vaccination.
- Intercurrent events and missing data: All data collected after or at intercurrent events will be excluded ([Section 2.2.2](#)). Antibody titers below the LLOQ, denoted as BLQ, or below the LOD will be set to $0.5 \times \text{LLOQ}$ for analysis ([Section 5.3.2](#)). Missing data will not be imputed. Immunogenicity data that are confirmed as not valid will not be used for analysis.

Reporting results:

- Descriptive statistics, including the sample size (n), HAI GMTs, HAI GMFRs, and 95% CIs for the HAI GMTs and HAI GMFRs, will be presented for each strain and each study intervention group ([Section 5.2.2](#)).

- Descriptive statistics, ie, HAI GMRs of each tIRV (tIRV2 and tIRV3) group compared with each control group (QIV2, QIV3, and qIRV2) at 4 weeks after vaccination, and the 95% CIs for the HAI GMRs, will be presented for each strain ([Section 5.2.2](#)).
- The proportion of participants achieving HAI seroconversion for each strain at 4 weeks after vaccination, and the associated 2-sided Clopper-Pearson 95% CIs, will be provided by study intervention group.
- The proportion of participants with HAI titers $\geq 1:40$ for each strain before vaccination and at 4 weeks after vaccination, and the associated 2-sided Clopper-Pearson 95% CIs, will be provided by study intervention group.
- Empirical RCDCs will be plotted by study intervention group.
- HAI GMTs for each strain, and the associated 95% CIs, will be plotted by study intervention group.
- HAI seroconversion rate for each strain, along with the associated 95% CIs, may be plotted by study intervention group.

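### Substudies A and B are meant to inform the choice of reformulation, but the readable SAPs plan no tIRV-versus-tIRV HAI ratio with its own confidence interval

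*SAP*

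**What the plan says.** Protocol 10.11.2.1 lists tIRV1, tIRV2 and tIRV3 and then states: "This substudy will inform the choice of the optimized influenza modRNA vaccine reformulation". Protocol 10.12.2.1 makes the same statement for tIRV2 and tIRV3 in older adults. Protocol 2.1 is more general: "The purpose of Substudies A and B is to evaluate the safety and immunogenicity of additional influenza modRNA vaccine candidates". The secondary objective in both substudies is to describe the immune response.

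For between-group HAI comparisons, section 6.2.1.1 of the Substudy A SAP plans "HAI GMRs of each tIRV (tIRV1, tIRV2 and tIRV3) group compared with each control group (QIV1, qIRV1) at 4 weeks after vaccination", with 95% CIs, for each strain. The Substudy B SAP, same section, plans "HAI GMRs of each tIRV (tIRV2 and tIRV3) group compared with each control group (QIV2, QIV3, and qIRV2" groups, also at 4 weeks. That is six ratios per strain in each substudy (3 × 2 in A, 2 × 3 in B), all of them tIRV against control. The method in SAP 5.2.2.3 is general: "The GMR will be calculated as the mean of the difference of logarithmically transformed assay results and exponentiating the mean". It is not tied to a control arm.

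Each group's n, GMT, GMFR and 95% CIs, seroconversion rate and reverse cumulative curve are also reported. Section 5.1 of both SAPs says "no formal statistical hypothesis testing will be performed. No decision rules will be applied", and the protocol adds "There is no multiplicity adjustment for Substudy A, as all analyses are descriptive in nature", with a matching statement for Substudy B.

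**The concern.** If a substudy is to help decide between formulations, the natural summary is the ratio of one formulation's titers to another's, with its precision. That row is absent from the readable plan. A reader comparing, say, tIRV2 with tIRV3 sees two GMRs that share a control arm, or two group GMTs with separate intervals. Neither display shows the uncertainty of the tIRV2/tIRV3 ratio. The control arm's sampling error widens both GMR intervals, yet it cancels from the difference between the two tIRVs. Differences between formulations can therefore look less resolved than the data make them. Conversely, one tIRV may appear to beat the control while another does not, although the two barely differ.

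**Working it through.** **The plan's own figure.** The only numerical support for the sample size is the probability of seeing at least one AE with n = 90 (Protocol Table 6; Table 8 is identical). 1 − (1 − p)^90 at p = 0.5, 1, 2, 5 and 7% gives 36.3, 59.5, 83.8, 99.0 and 99.85%, which matches the table (99.9% for the last). 5 × 90 = 450 also agrees. No precision or power is stated for any HAI ratio.

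**Inputs.** Equal groups of about 90 (Protocol 10.11.9.5 and 10.12.9.5) and two-sided 95% intervals (SAP 5.2). The SD of log titer and the evaluable number per arm are not given, so they are assumed where needed.

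**Step 1, SD-free comparison.** With n per arm and SD s on the log scale, the log ratio of any two arms has SE = s√(2/n). This is the same for tIRV/tIRV and tIRV/control. Using normal approximations:
- Direct tIRV/tIRV interval excludes 1 when the observed log ratio exceeds 1.96 SE.
- Two GMT intervals fail to overlap when it exceeds 2 × 1.96 × s/√n = 3.92 SE/√2 = 2.77 SE.
- Two GMR intervals on the same control fail to overlap when it exceeds 2 × 1.96 SE = 3.92 SE.

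Taken as two-sided tests, the two overlap readings have alphas of about 0.0056 and 0.0001.

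**Step 2, power.** A direct contrast has 80% power at a true difference of 1.96 + 0.84 = 2.80 SE. At that difference:
- GMT non-overlap: P(Z > 2.77 − 2.80) = 51%.
- GMR non-overlap: P(Z > 3.92 − 2.80) = 13%.

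**Step 3, fold scale.** Assume 85 evaluable per arm and an SD of 1.4 to 2.2 log2 titer. SE = 1.4√(2/85) = 0.215 up to 2.2√(2/85) = 0.337.
- Observed ratio at which the direct CI just excludes 1: 2^(1.96 × SE) = 1.34 to 1.58.
- True ratio for 80% power: 2^(2.80 × SE) = about 1.52 to 1.93.
- Observed ratio for GMR-interval non-overlap: 2^(3.92 × SE) = 1.79 to 2.50.

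The first and third are observed ratios; only the second is a power statement. A true difference equal to the first is detected only about half the time.

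**Step 4, check under other assumptions.** With 90 per arm, t intervals and a log10 SD of 0.5 (0.5/0.301 = 1.66 log2), the observed ratios needed are 1.40 (direct), 1.62 (GMT non-overlap) and 1.97 (GMR non-overlap). For a true ratio of 1.5 the chances are 66%, 33% and 6%.

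**Step 5, the opposite error.** Same assumptions, 400,000 simulated trials, two equal tIRVs each truly 1.4-fold above the control: exactly one of the two control-GMR intervals lies above 1 in 33% of trials. The direct interval wrongly excludes 1 in about 5%. The 33% depends on the assumed SD and true ratio.

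**Step 6, what can be rebuilt.** For each group, SE_i = (log upper − log lower)/(2t), with t on n_i − 1 degrees of freedom. The tIRV/tIRV ratio is the ratio of the two GMTs, and its SE is √(SE_i² + SE_j²). The planned output is sufficient for this.

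**The case against.** The case against is substantial. The stated purpose in Protocol 2.1 is to evaluate candidates, the objective is to describe, and the design compares tIRVs with licensed vaccine and qIRV, so the control GMRs answer the comparison that the protocol sets up. Informing a choice is an intended use, and performance against the controls and safety (the primary objective) bear on it too. All of this stands.

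A reader might infer three stronger things, none of which the documents support:
- **That a tIRV-versus-tIRV contrast is planned nowhere.** The text after section 6.3.3 is redacted in both SAPs, so only the readable text can be judged.
- **That the choice will be read from the wrong intervals.** No decision rule is set and nothing tells anyone to judge by overlap. The sponsor also has unblinded reviews (SAP 7.1), with dose selection a named purpose.
- **That the planned output cannot yield the contrast.** It can, as Step 6 shows.

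The 13% is the extreme case; the more natural side-by-side reading of GMT intervals gives 51%.

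What does not stand is that a descriptive plan has no place for such a row. The SAPs already present control GMRs with 95% CIs as descriptive statistics, without a hypothesis or multiplicity adjustment. Pairwise tIRV GMRs would have the same standing.

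**Conclusion.** The point holds as an omission from the readable plan: both substudies are said to inform the choice of reformulation, and no direct tIRV/tIRV HAI ratio with its own CI is listed. No stated figure is wrong and no stated estimand lacks its analysis. The loss is a prespecified, displayed interval; the information itself is retained. The multiples of 1.96, 2.77 and 3.92 SE, and the 80%, 51% and 13% that follow, rest on equal arms, a common SD and normal approximations, but not on the size of the SD. The fold figures rest on the assumed 85 evaluable per arm and SD of 1.4 to 2.2 log2. The power losses apply only to a reader who actually judges by overlap. The addition is worth making because it costs almost nothing and shows how precisely the formulations can be told apart.

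**What to change.** In section 6.2.1.1 of the Substudy A SAP, add 4-week HAI GMRs with 95% CIs, per strain, for tIRV1 vs tIRV2, tIRV1 vs tIRV3 and tIRV2 vs tIRV3. In the same section of the Substudy B SAP, add tIRV2 vs tIRV3. Use the GMR method already in 5.2.2.3 and keep the control GMRs.

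Label the new rows descriptive. Do not state that selection rests on them alone: that would introduce a decision rule that section 5.1 disclaims and would leave out the primary safety data. Add a note that groups need not be open for randomization over the same period (Protocol 10.11.4.1 and 10.12.4.1). That caveat applies equally to the control GMRs.

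The cost is a few lines of SAP text and extra table rows, three per strain in A and one per strain in B. No new data, participants or methods are needed.

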6.2.1.2. Sensitivity/Supplementary Analysis

To support the assessment of immunogenicity, estimands as specified in [Section 2.2.2](#) using the treatment policy strategy might be summarized with the mITT immunogenicity population (HAI CCI [REDACTED]) using the same presentation as specified in the main analysis.

6.3. Other Safety Summaries and Analyses Endpoint(s)

6.3.1. Data Collected on the Summary of Reactogenicity CRF Page

Data collected about reactogenicity events on the Summary of Reactogenicity CRF page will be summarized or listed.

The main reasons for noncompletion of the 7-day reactogenicity event reporting (including e-diary entries and the data on the Participant Reported Reactogenicity CRF page) will be listed.

Immediate reactogenicity events may be summarized by study intervention group. The medically attended reactogenicity events will be listed.

6.3.2. Medical History

Each reported medical history term will be mapped to an SOC and PT according to MedDRA. The number and percentage of participants with an assigned vaccine having at least 1 diagnosis of medical history, overall and at each SOC and PT level, will be summarized by study intervention group and for all participants in total based on the safety population.

6.3.3. Electrocardiograms

The data collected for study participants who report any symptom(s) that might be indicative of myocarditis or pericarditis within 28 days after a study vaccination (ECG, troponin I level, cardiac echocardiogram, and/or cardiac magnetic resonance study) will be summarized and listed by vaccine group.

CCI

090177e1a0eba359\Approved\Approved On: 13-Jun-2024 14:08 (GMT)

CCI

090177e1a0eba359\Approved\Approved On: 13-Jun-2024 14:08 (GMT)

CCI

6.5. Subset Analyses

Subset analyses will be performed for safety primary endpoints and immunogenicity secondary endpoint by age subgroups (18-49 years; 50-64 years). The main analysis described for these endpoints in [Section 6.1.1.1](#), [Section 6.1.2.1](#), and [Section 6.2.1.1](#) will be performed by the age subgroups.

6.6. Baseline and Other Summaries and Analyses

6.6.1. Baseline Summaries

Descriptive summary statistics for demographic characteristics (age at vaccination, sex, race, and ethnicity) will be generated by study intervention group and for all participants in total based on the safety population.

6.6.2. Study Conduct and Participant Disposition

6.6.2.1. Participant Disposition

All participants in the randomized population will be included in the disposition summaries. Summaries will be displayed by vaccine group separately.

The number and percentage of randomized participants will be included in the participant disposition summary. In addition, the number and percentage of participants who received vaccinations, completed the follow-up visits, and withdrew before the follow-up visit, along with the reasons for withdrawal, will be tabulated by study intervention group and the total sample. The reasons for withdrawal will be those as specified in the database.

Participants excluded from each analysis population will also be summarized separately by study intervention group, along with the reasons for exclusion by study intervention group.

A listing of protocol deviations may also be provided.

6.6.2.2. Blood Samples for Assay

For each blood sampling time point, the number and percentage of randomized participants providing blood samples within the protocol-specified time frame, as well as before and after the protocol-specified time frame, will be tabulated separately by study intervention group.

6.6.2.3. E-Diaries

The participants who were vaccinated and who transmitted and completed e-diaries will be summarized according to the vaccine actually received. Besides the analysis described in [Section 6.1.1](#), the summary will also include the number and percentage of vaccinated participants not transmitting the e-diary, transmitting the e-diary, and completing the e-diary for any day (based on the e-diary completion category as defined in [Section 3.5.2](#)) in the required reporting period after vaccination by assigned study intervention.

The number and percentage of participants transmitting and completing the e-diary for each day in the required reporting period, and overall, will be tabulated for each study intervention group.

The safety population will be used.

